4.6.5 Analysis of Exploratory Efficacy Endpoints

Continuous Exploratory Efficacy Endpoints

Continuous endpoints include change from baseline of the following outcomes:

- Weekly CSBM rate during the Placebo Withdrawal and Washout periods
- Weekly SBM rate during the Placebo Withdrawal and Washout periods
- Stool ease of passage during the Placebo Withdrawal and Washout periods
- Stool consistency during the Placebo Withdrawal and Washout periods
- Suppository/enema use during Placebo Withdrawal and Washout periods
- Total score and 3 subdomain scores from PAC-SYM during the Placebo Withdrawal and Washout periods
- Total Score and 4 subdomain scores from PAC-QoL during the Placebo Withdrawal and Washout periods
- Stool microbiome during each study period, defined as the number of species found in the microbiome

- Total sleep time (hours) per day during each study period
- Delay (minutes) in sleep onset per night during each study period
- Total awake time (hours) per night during each study period
- Number of wakes per night during each study period
- Total score from UPDRS and individual part scores to assess the symptoms of Parkinson's Disease during each study period
- Total score from BDI-II to assess the intensity of depression during each study period
- Total score from MMSE to assess cognition during each study period

All continuous exploratory efficacy endpoints will be analyzed in the same manner as the primary efficacy endpoint with treatment, baseline CSBM strata, and corresponding baselines as the independent variables in the ANCOVA model. Changes to the single blind placebo and washout periods will also be repeated using the fixed dose rate or end of fixed dose measurement as baseline. Summary statistics will also be presented by specific fixed dose groups for descriptive purposes only.

Categorical Exploratory Efficacy Endpoints

The following is the lone categorical exploratory efficacy endpoint:

- Improvement in frequency and/or severity of hallucinations/delusions as measured by SAPS-PD score during the Fixed Dose period over baseline for subjects with SAPS-PD score >0 at the Screening visit. Improvement is defined as ≥ 2.33 points reduction in score from baseline on the SAPS-PD

The endpoint will be analyzed using Fisher's exact test, and also by the Cochran-Mantel-Haenszel (CMH) test adjusting the baseline CSBM strata, if numbers permit, to compare ENT-01 versus placebo. Summary statistics will also be presented by specific fixed dose groups for descriptive purposes only.

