- Improvement in cognition as assessed by the MMSE: The MMSE is an 11-item examination with a score ranging from 0 – 30 with a higher score indicating better memory. The MMSE will be summarized over time.
- Change in plasma L-Dopa levels 20, 40, and 60 minutes after L-Dopa and ENT-01 dose: An increase of >30% in peak plasma level during treatment versus baseline would indicate clinically significant increase in absorption attributable to ENT-01 (20 subjects).
- Change in stool microbiome during treatment: Since ENT-01 has antimicrobial properties in vitro, it may alter the intestinal microbiome; the subject's stool will be analyzed for common intestinal bacteria and viruses at Baseline and Fixed Dose, periods (20 subjects). If subjects discontinue from the study prior to the end of the Fixed Dose period, stool will be collected and analyzed at the Early Termination visit, as applicable.

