- Stool and laxative Diary Instructions: Subjects will be taught how to use the I-Pad for stool and laxative diaries. They will be instructed to take the I-Pad to the toilet and fill it in immediately after a bowel movement. They will be taught the definition of a CSBM. If the subject “feels like he/she is completely emptied out” and that “they have no more stool left to pass”, and the stool is not just a few pebbles, then that will be a CSBM (a complete BM). If the subject leaves the house for a few hours, they will be told to take the I-Pad with them in case they have a BM elsewhere. Each BM will be entered immediately. If no entries have been made for the day, the subject will be sent 3 reminders starting at 7pm. Laxative use will also be entered immediately into the laxative diary. Multiple uses will be entered multiple times.
- AE Review
- Prior and Concomitant Medication
- Rome IV questionnaire
- MDS-UPDRS – The MDS-UPDRS should be administered while the subject is in an ON state, approximately one hour after taking levodopa (if applicable). If the “on” time is earlier or later than 60 minutes after L-Dopa, UPDRS will be performed at that time.
- Subjects will be invited to participate in two sub-studies, consisting of obtaining levodopa PK draws pre-dose, and 20, 40 and 60 minutes post-dose at Visits 2 and 3, 4, 5 and 6 and (2) stool sample collection on Visits 2 and 4. This first twenty subjects to affirm consent will participate in the L-Dopa sub-study and the first 20 subjects to affirm consent will participate in the stool microbiome study.
- Questionnaires:
 - C-SSRS
 - SAPS-PD and hallucination interview (only those subjects who have a SAPS-PD score > 0 at the Screening Visit and Randomization Visit).
 - BDI-II
 - MMSE

- Dispense Stool Collection Kit – Subjects participating in the sub-study will be given a stool collection kit so they can bring a stool sample at Visit 2

For subjects who score > 0 on the SAPS-PD at Visit 1 and Visit 2, the SAPS-PD and hallucination interview are repeated at Visit 2.

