9.2.4.2 Secondary Efficacy Endpoint Analyses

Secondary efficacy analyses will be based on the Efficacy Evaluable Population. The comparison of active versus placebo treatment will be tested at the two-sided 0.05 significance level.

The following are the set of continuous secondary efficacy endpoints:

- Change from baseline in the weekly SBM rate during the Fixed Dose period
- Change from baseline in stool ease of passage during the Fixed Dose period
- Change from baseline in stool consistency during the Fixed Dose period
- Change from baseline in suppository/enema use during the Fixed Dose period

All continuous secondary efficacy endpoints will be analyzed in the same manner as the primary efficacy endpoint.

The following are the set of dichotomous secondary efficacy endpoints:

- Pro-kinetic bowel response during the Fixed Dose period
- SBM bowel response to ENT-01 during the Fixed Dose period

For the dichotomous secondary efficacy endpoints, the comparison of the ENT-01 versus placebo treatment groups will be performed by means of Fisher's exact test.

The following are the set of time to event secondary efficacy endpoints:

- Time to first CSBM in the Fixed Dose period
- Time to first SBM in the Fixed Dose period
- Time to first rescue medication use in the Fixed Dose period
- Time to event secondary efficacy endpoints will be summarized using Kaplan-Meier methods, comparisons between treatment groups will be made via log-rank tests.
- For the frequency of dose adjustments in the Dose Adjustment period secondary endpoint, the frequency of the number of dose adjustments a subject has from the initial starting dose to the subject's fixed dose will be summarized by treatment group and baseline CSBM strata.
- For the PAC-SYM and PAC-QOL subjective assessments secondary efficacy endpoints, the overall scores from the Fixed Dose period will be analyzed via an ANCOVA model with treatment as a factor and the subject's corresponding baseline score as a covariate. Additional summaries of the individual items will be performed.

9.2.4.3 Exploratory Efficacy Endpoint Analyses:

The analysis methods for the exploratory efficacy endpoints will be provided in the SAP.

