1.2.3 Exploratory Objectives

The exploratory objectives include:

- To determine the decrease in efficacy in the blinded placebo withdrawal and washout periods.
- To collect information on the effect of ENT-01 on motor and non-motor symptoms of Parkinson's disease including mood, memory, sleep, and hallucinations/delusions.
- To collect information on the effect of ENT-01 on levodopa absorption.
- To collect information on the effect of ENT-01 on the stool microbiome.

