- Improvement in sleep as assessed by sleep diaries.
- Change in plasma L-Dopa levels 20, 40, and 60 minutes after L-Dopa and ENT-01 dose: An increase of >30% in peak plasma level during treatment versus baseline would indicate clinically significant increase in absorption attributable to ENT-01 (10 subjects only).
- Change in stool microbiome during treatment: Since ENT-01 has antimicrobial properties in vitro, it may alter the intestinal microbiome; the subject's stool will be analyzed for common intestinal bacteria and viruses at Baseline, Fixed Dose, and Washout periods (10 subjects only).

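### Species number, the SAP's only microbiome measure, detects net loss or gain of species but not replacement, so it answers only part of the protocol's question

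*SAP*

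**What the plan says.** The objective is open-ended: "To collect information on the effect of ENT-01 on the stool microbiome" (SAP 1.2.3). The protocol's reason for it is that "Since ENT-01 has antimicrobial properties in vitro, it may alter the intestinal microbiome" (Protocol 3.3). No direction or type of alteration is named.

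The protocol leaves the method to the other document: "The analysis methods for the exploratory efficacy endpoints will be provided in the SAP" (under Protocol 9.2.4.3). The SAP's only definition, in 4.6.5, is "Stool microbiome during each study period, defined as the number of species found in the microbiome". The model follows from "All continuous exploratory efficacy endpoints will be analyzed in the same manner as the primary efficacy endpoint", with treatment, baseline CSBM stratum and the corresponding baseline as terms. Neither document gives a dissimilarity, a per-taxon comparison, an abundance measure or a diversity index. The separate SAP announced in SAP 2.6.4 is for PK only.

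Sampling is described in different ways:
- Protocol 3.3: "common intestinal bacteria and viruses at Baseline and Fixed Dose, periods (20 subjects"). Protocol 4.1 agrees on timing: "stool sample collection on Visits 2 and 4".
- SAP 2.6.3: baseline, "Fixed Dose, and Washout periods (10 subjects only").
- SAP Table 1 marks stool collection at Visits 2 and 4 only. Protocol Table 1 and Appendix 2 add Early Termination.

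**The concern.** An agent with antimicrobial activity could change the gut flora in at least three ways: fewer species overall, different species in place of those lost, or altered abundance among species that stay. The planned measure sees only the first. If the effect is mainly replacement, the ANCOVA on species number would reject at about its false-positive rate, and the sub-study would have nothing else prespecified to show the change.

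The samples are paired before and after treatment. Counting species normally requires identifying them, so the information needed to measure replacement is probably in hand but not used.

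A second problem stands apart from the choice of measure. Section 4.6.5 asks for results in every study period, but no stool is scheduled at Visits 5 or 6. The placebo-withdrawal and washout results therefore cannot be produced from the schedule as it stands.

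**Working it through.** The documents give no power, species number or variability for this endpoint, so there is no figure of theirs to reproduce. The check has three parts.

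**1. Arithmetic of the definition.** Let a subject have S species at baseline, lose k and gain k.
- Change in count = (S - k + k) - S = 0.
- Jaccard dissimilarity = 1 - (S - k)/(S + k).
- With k equal to 10%, 20%, 30% and 50% of S, the count changes by 0 each time and the dissimilarity is 0.18, 0.33, 0.46 and 0.67. For example, with S = 100 and k = 30: 1 - 70/130 = 0.46.

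If losses exceed gains, the count falls by the difference, so it does respond to net loss.

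**2. Illustration of power.** From the documents: 20 subjects (Protocol 3.3) or 10 (SAP 2.6.3), ANCOVA on change, two-sided 0.05 (SAP 4.2). Assumed, not in the documents:
- an equal split between arms;
- baseline species number S about Normal(100, SD 15);
- each subject's natural turnover t averaging 20% or 30%, with an SD between subjects of 5 points unless stated;
- species lost ~ Binomial(S, t + extra loss) and gained ~ Poisson(S × (t + extra gain)), with the extras in the ENT-01 arm only.

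The count is tested by ANCOVA on arm and baseline count (adding a randomly assigned CSBM stratum makes no material difference). Jaccard is tested by Mann-Whitney. Figures are rounded, and repeated runs differ by a few points.

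| Extra change on ENT-01 | Natural turnover (SD) | Per arm | Count | Jaccard |
|---|---|---|---|---|
| Replacement, +10 to +20 points | 20-30% (5) | 10 | about 5% | about 90-100% |
| Loss only, 10 points | 20-30% (5) | 10 | about 78-89% | about 56% |
| Loss +15, gain +10 points | 20% (5) | 10 | about 32% | about 99% |
| Replacement, +10 points | 20% (10) | 10 | about 5% | about 50% |
| Replacement, +10 points | 20% (15) | 10 | about 5% | about 28% |
| Replacement, +10 points | 20% (5) | 5 | about 5% | about 54% |

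With no drug effect, the Jaccard test rejects in about 4% of trials, so its error rate is sound.

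A hand check supports the loss-only row for the count. At 20% turnover, the variance of the change is about 100 × 0.2 × 0.8 + 100 × 0.2 = 36 on placebo and 100 × 0.3 × 0.7 + 100 × 0.2 = 41 on ENT-01. The common SD is about √38.5 = 6.2, so a mean difference of 10 species is 10/6.2 = 1.6 SD. With 10 per arm, 80% power needs about (1.96 + 0.84) × √(2/10) = 1.25 SD.

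**3. Sampling, side by side.** SAP 4.6.5 needs a sample in every period, and SAP 2.6.3 needs baseline, fixed dose and washout. The SAP's own schedule supplies Visits 2 and 4. Its footnote on stool collection alludes to a washout visit, but the grid has no such sample. The subject numbers, 10 and 20, also disagree.

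**The case against.** The strongest reply is that the near-zero power of the count is built into the scenario. Equal loss and gain is the one case in which the expected change in count is zero. The documents' rationale is antimicrobial activity, for which net loss of species is at least as natural an alternative, and there the count does better than Jaccard. This stands. A reader might infer that the planned analysis has almost no power against any change in composition, or that dissimilarity should replace the count. The documents support neither: they do not say what kind of change is expected, and for pure loss, replacing the count would install the weaker test.

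The advantage of Jaccard also depends on an undocumented SD and on 10 subjects per arm, and it shrinks quickly when either is less favourable. The equal split is itself assumed: Protocol 4.1 takes the first 20 to consent, and randomization is not stratified by sub-study membership. This stands too, and is why the table shows the range.

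The assay is not described. If it is a fixed panel of common organisms, gains are bounded and 100 species is only a placeholder. That species identities are available is an inference, though a reasonable one.

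Finally, the stakes are low: an optional exploratory sub-study, with trial success resting on the CSBM analysis (SAP 4.6.3). A reader might also infer that a null count would be reported as no effect on the microbiome. Neither document says so. None of this removes the arithmetic point that replacement is invisible to the only measure defined.

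**Conclusion.** The point holds as one of incomplete coverage. Species number is a legitimate summary and detects net loss or gain, but it cannot register replacement, nor shifts in abundance among species that persist. It therefore answers part of the protocol's question. The arithmetic needs no assumptions. The power figures do, and they run in both directions: about 5% against 90-100% in favour of Jaccard for balanced replacement, and about 78-89% against 56% in favour of the count for 10 points of pure loss, both at 10 per arm with a turnover SD of 5 points. Neither measure covers both alternatives well, which is the case for having both.

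The mismatch between the periods to be analysed and the samples scheduled, and between 10 and 20 subjects, is a plain inconsistency that does not depend on any simulation.

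The importance is low. The endpoint is exploratory and the primary conclusion is not touched.

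**What to change.** In SAP 4.6.5:
1. Keep change in species number as planned.
2. Add, as a co-equal exploratory measure, each subject's dissimilarity between Visit 2 and Visit 4: Jaccard on presence/absence, or Bray-Curtis if the assay reports abundances. Compare arms by a Wilcoxon or permutation test.
3. For this endpoint, replace the reference to every study period with baseline (Visit 2) and end of treatment (Visit 4, or Early Termination).

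In SAP 2.6.3, reconcile the 10 subjects and the washout sample with the 20 subjects and the baseline and fixed-dose sampling in Protocol 3.3, and bring the stool row and footnote of SAP Table 1 into line.

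The cost is wording and one short analysis of samples already scheduled, with no new visits or collections. The downside is one more exploratory p-value without adjustment; SAP 4.2 makes no multiplicity adjustment anywhere, so nothing is taken from the primary test. The change should be made before treatment codes are available to those who write it.

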The purpose of the treatment period is to establish the impact of ENT-01 on CSBM rates. The purpose of the placebo period is to determine the duration of the treatment effect once study medication is discontinued. At this visit, all subjects will be given placebo and will continue taking the same number of tablets as they were taking at the maximum “fixed” dose period. The subject will not be made aware that the study medication provided is a placebo.

During this visit, the following assessments and procedures will be performed:

- Brief Physical Exam
- Weight
- Orthostatic Vital Signs – 3 sets: See screening description
- 12-lead ECG
- Labs and urinalysis as defined in [APPENDIX 1](#).
- Pregnancy Testing - For women of child-bearing potential only.
- IP/Placebo Collection and Accountability
- Single-blind Placebo Dispensation
- For subjects participating in the L-Dopa sub-study, subjects will be instructed to come to clinic as early as possible and on an empty stomach. They will first take their study medication (ENT-01 or placebo) in clinic. Thirty minutes after the ENT-01/placebo dose, subjects will take their morning dose of levodopa.
- Levodopa PK Draws - Blood samples will be obtained before the -L-Dopa dose and at 20,

40 and 60 minutes after the dose

- IP/Placebo Collection and Accountability
- Dispense Rescue Medication, as needed. Subjects continue appropriate use of rescue medication, ensuring adequate bowel movements every 3 days.
- Stool Diary Review
- AE Review
- Prior and Concomitant Meds
- MDS-UPDRS - The MDS-UPDRS should be administered while the subject is in an ON state, approximately one hour after taking levodopa (if applicable), or whenever “ON” occurs.
- Questionnaires:
 - C-SSRS
 - BDI-II
 - MMSE
 - PAC-SYM
 - PAC-QOL
 - SAPS-PD and hallucination questionnaire (if applicable)
- Collect Stool Sample (if applicable)

4.5 Visit 5: End of placebo period/ beginning of Wash-Out (Study Day 39) (+/- 8 days)

The purpose of the Wash-out period is to determine the duration of treatment effect. Subjects will be taken off placebo (study medication). They will continue to keep daily stool diaries for the duration of this period. During the first 3 weeks, subjects will continue to use rescue medication as needed. The following day, i.e., day 22 of the Wash-Out Period, subjects will be instructed to restart all their original medications, including oral laxatives.

During this visit, the following assessments and procedures will be performed:

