9.2.5 Sample Size/Power Considerations

Sample size for this study was determined based on the results from the phase 2a study. In the phase 2a study, efficacy was demonstrated in 34 subjects treated with ENT-01, with a mean change from baseline in CSBMs of 2.4. In that study, of the 72 randomized subjects, 64 (89%) were evaluable for the primary efficacy endpoint analysis. Randomization was 3:1 to active treatment or placebo; 64

subjects were randomized to active treatment and 18 subjects were randomized to placebo. The study assumed an increase from baseline in weekly CSBM rate in the Fixed Dose period of 2.4 and 0.5 for the active drug and placebo-treated subjects, respectively, and an SD of 2.0. amended.

In this protocol amendment, enrolling an additional 80 subjects in a 1:1 randomization will yield a conditional power of approximately 93% and an additional 60 subjects will yield a conditional power of 88%. This is based on the additional subjects having a least squares mean change from baseline for the Fixed Dose Period of 3.55 and 1.28 for ENT-01 and placebo, respectively, and a common standard deviation of 3.88. The power calculations incorporated a 10% drop-out rate. These parameter estimates and conditional power calculations are based on the results of the initial cohort of subjects in the Phase 2b study.

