2. STUDY DESIGN

2.1. Synopsis of Study Design

This study will be conducted as a multicenter, randomized, double-blind, placebo-controlled study in patients with Parkinson's Disease and constipation.

This study has two parts. The first part of this randomized approximately 72 subjects in a 3:1 to treatment or placebo ratio (double-blind), with approximately 54 subjects allocated to the treatment groups and approximately 18 to placebo. In the second part of the study, an additional 80 patients (approximately) will be randomized 1:1 to treatment or placebo (double-blind) with approximately 40 subjects allocated to each group.

In both parts of the study, the study was conducted as a multicenter, randomized, double-blind, placebo-controlled study. A subject's total study duration was no more than 10 weeks and total active dosing days was a maximum of 25 days.

During the active dosing period, patients will be able to increase/adjust their dose every three days. This is called the Dose Adjustment period. After the subject documents two complete spontaneous bowel movements in three days, the subject will fix at the dose for the remainder of the study. This is called the Fixed Dose period. After completing up to 25 days of dosing, all subjects will be given placebo for 2 weeks (single-blind) followed by 4 weeks of wash-out.

Figure 1. Visit Schedule Overview					
Visit 1	Visit 2	Visit 3	Visit 4	Visit 5	Visit 6
Screening	Randomization and Drug Dispensation	Follow up	Single Blind Placebo Withdrawal	Wash Out	End of Study
Day -14	Day 1	Day 11 +/- 1 day	Day 25 - 3 days	Day 39 +/- 2 days	Day 69 +/- 3 days

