4.6.3 Analysis of the Primary Efficacy Endpoint

The primary efficacy endpoint is the change from baseline in weekly CSBM rate during the Fixed Dose period. The primary analysis will be based on the Fixed Dose Population. The primary efficacy analysis will be performed via an analysis of covariance (ANCOVA) model with change from baseline in weekly CSBM rate as the dependent variable, treatment (ENT-01 or placebo) as the independent variable, and baseline weekly CSBM rate as a covariate.

As a supplemental analysis, the treatment effect for the primary efficacy endpoint will be summarized by the weekly CSBM rate subgroups (0 – 0.9, 1.0 – 3.0). The analysis will be performed for both Efficacy Evaluable population and Fixed Dose population.

The study will be considered a success if the p-value for the comparison of treatment groups from the ANCOVA model using the Fixed Dose population is significant (p<0.05).

Change from baseline in weekly CSBM rate will also be summarized by the specific fixed dose for patients. These summaries will be descriptive in nature only and no inferential statistics will be performed.

A linear trend test for weekly CSBM rate within each treatment group across baseline, fixed dose, and single blind periods will be conducted by using mixed model repeated measures (MMRM) methods, where the Baseline, Fixed Dose, and Single Blind periods are assigned values of 0,1, and 2 respectively for modeling purposes. Baseline CSBM rate (0-0.9/1.0-3.0) is included as a factor, with subject intercept and slope as random effects in the mixed model. The trend test will also be conducted across all subjects, including both Placebo and ENT-01 treatment groups in the model as a factor (fixed effect).

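### The repeat withdrawal and washout ANCOVA appears to adjust for the on-drug Fixed Dose value, so its treatment coefficient measures neither the difference after stopping nor the loss of effect

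*SAP*

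**What the plan says.** SAP 4.6.5 analyses the continuous exploratory endpoints in the same way as the primary endpoint, with "treatment, baseline CSBM strata, and corresponding baselines as the independent variables in the ANCOVA model". The next sentence adds that changes to the single-blind placebo and washout periods "will also be repeated using the fixed dose rate or end of fixed dose measurement as baseline". It names no different model and does not restrict the repeat to description, although the sentence after it does restrict the summaries by fixed dose to description.

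In the primary analysis (SAP 4.6.3) the corresponding term is "baseline weekly CSBM rate as a covariate", a pre-treatment value.

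SAP 1.2.3 gives the aim: "To determine the decrease in efficacy in the blinded placebo withdrawal and washout periods". Protocol 4.4 (Visit 4) puts it this way: "The purpose of the placebo period is to determine the duration of the treatment effect once study medication is discontinued". After the Fixed Dose period "all subjects will be given placebo for 2 weeks (single-blind) followed by 4 weeks of wash-out", so both arms are off active drug in the periods concerned.

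SAP 4.2 and 4.6 test efficacy endpoints at two-sided 0.05 without multiplicity adjustment. Protocol 9.2.4.3 leaves the exploratory methods to the SAP.

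**The concern.** A baseline covariate is safe in a randomized comparison because treatment cannot have changed it. The Fixed Dose rate is different: it is measured on treatment and it forms the primary outcome. Holding it fixed compares ENT-01 subjects with placebo subjects who reached the same on-treatment rate without drug. Those placebo subjects are an unusually high-rate subset, and randomization does not balance the two groups.

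At stake is what the trial reports about how the effect fades. A reader who takes the coefficient as the difference between arms after stopping could see ENT-01 below placebo when the arms are level, or no difference when part of the benefit persists. A reader who takes it as the loss of effect would see too small a loss. At least seven listed endpoint families are affected, over two periods.

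**Working it through.** **The plan's own figures.** The documents give no power or effect figure for the withdrawal or washout analyses, so none can be reproduced here. As a check on the inputs, the Part 1 power in SAP 4.1 (90%; difference 2.4 - 0.5 = 1.9, SD 2.0, 64 evaluable at 3:1, so 48 vs 16) recomputes to 90.0% with a noncentral t.

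**Inputs from the documents**
- On-drug difference: Protocol 9.2.5 plans on a "Fixed Dose Period of 3.55 and 1.28 for ENT-01 and placebo, respectively, and a common standard deviation of 3.88". So D = 3.55 - 1.28 = 2.27 CSBM per week.
- SAP 4.1 gives SDs of 4.11 (ENT-01) and 2.38 (placebo).
- All of these SDs describe change from baseline in the Fixed Dose period. Applying them to Fixed Dose and withdrawal rates is an assumption.

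**Assumed, not in the documents**
- Within-arm correlation r between Fixed Dose and withdrawal rates of 0.3, 0.5 or 0.7.
- Analysis sizes of 36 vs 36 (Part 2 after 10% dropout), or 84 vs 52 if both parts are combined (48 + 36 vs 16 + 36).

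**Step 1: what the coefficient estimates.** Let W be the true arm difference in withdrawal rate. With the Fixed Dose value as covariate, modelling the change or the raw withdrawal rate gives the same treatment coefficient:

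coefficient = W - b x D, where b = r x SD(withdrawal) / SD(Fixed Dose).

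This can be rewritten as (1 - b) x W + b x (W - D). It is a weighted mix of the difference in withdrawal rates (W) and the between-arm loss of effect (W - D), and the weight b depends on the correlation, not on the question asked.

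**Step 2: full wear-off (W = 0), SD 3.88 in both periods, so b = r.**

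| r | Coefficient | True difference in withdrawal rate | True difference in change from Fixed Dose |
|---|---|---|---|
| 0.3 | -0.3 x 2.27 = -0.68 | 0 | -2.27 |
| 0.5 | -0.5 x 2.27 = -1.14 | 0 | -2.27 |
| 0.7 | -0.7 x 2.27 = -1.59 | 0 | -2.27 |

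Simulation with the CSBM stratum in the model (4,000 trials per setting; pre-treatment SD 0.9 and correlation 0.3 with later rates, both assumed) gives about -0.6, -1.06 and -1.55. A significant result with ENT-01 lower occurred in 9.7%, 24.8% and 60.3% of trials at 36 vs 36, and in 14.1%, 40.2% and 85.2% at 84 vs 52. For a comparison of withdrawal rates the nominal figure in that direction is 2.5%. The planned model with the pre-treatment baseline gave a mean of 0.0 and rejected in 4.6% to 5.6% of trials.

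**Step 3: smaller spread after stopping.** If the extra ENT-01 variance is drug response, it may vanish at withdrawal, leaving an SD of about 2.38.
- Fixed Dose SD kept at 3.88: b = r x 2.38 / 3.88 = 0.184, 0.307, 0.429, so the coefficient is -0.42, -0.70, -0.97.
- Fixed Dose SDs 4.11 and 2.38, correlation r in each arm, 36 vs 36: pooled variance = (4.11² + 2.38²) / 2 = 11.28; pooled covariance = r x (4.11 x 2.38 + 2.38²) / 2 = 7.72r; b = 0.685r; coefficient -0.47, -0.78, -1.09.
- Same SDs, but the drug-response part unrelated to later rates, 84 vs 52: pooled variance = (84 x 4.11² + 52 x 2.38²) / 136 = 12.60; covariance = 2.38² x r = 5.66r; b = 0.450r; coefficient -0.31, -0.51, -0.71.

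Together these run from roughly -0.3 to -1.1.

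**Step 4: half the effect kept.** W = 1.135, r = 0.5, equal SDs: 1.135 - 0.5 x 2.27 = 0. Simulated with the stratum, the coefficient averages +0.06 (36 vs 36), while the pre-treatment model recovers 1.13.

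**Step 5: when there is no problem.** With D = 0 the repeat averages 0.00 and rejects in 5.1% of trials (36 vs 36, r = 0.5). With r = 0 there is no bias against ENT-01 (simulated mean +0.15 to +0.16; rejections 5.3% to 5.9%).

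**The case against.** Four points deserve weight.

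**The covariate role is inferred.** The repeat sentence names a new baseline and no model. The value might serve only to form the change. That stands as an uncertainty. On that reading the between-arm difference under full wear-off is 0 - 2.27 = -2.27, a correct loss of effect, and only labelling is needed.

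**Zero is not the only benchmark.** The stated aim is the decrease in efficacy, and under full wear-off ENT-01 does fall 2.27 further than placebo. A negative coefficient then points the right way. This stands: the rejection rates in Step 2 are false positives only if the result is read as a comparison of rates after stopping. It does not rescue the adjusted coefficient, which understates the loss.

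**The size depends on inputs that the documents do not give.** This stands. The correlation is assumed, and with the SAP's unequal SDs the estimate can be about half as large.

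**Little hangs on it.** The analysis is exploratory, a sound analysis sits beside it, and SAP 4.6.3 ties study success to the Fixed Dose comparison alone. This limits the importance.

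A reader might also infer that the repeat makes ENT-01 look worse whenever the arms are equal. The documents do not support that. If the arms are equal throughout there is no bias. It needs a difference on drug, which the sample size assumes, and a positive within-arm correlation, which is plausible for repeated counts in one person but is not stated.

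**Conclusion.** The concern holds in a limited form. On the natural reading of SAP 4.6.5, the repeat ANCOVA conditions on an outcome of treatment, and its coefficient answers neither of the two questions that the withdrawal and washout periods can answer. Under the planned on-drug difference, complete wear-off and correlation 0.3 to 0.7, it is about -0.7 to -1.6 CSBM per week with equal SDs of 3.88, or roughly -0.3 to -1.1 with withdrawal SD near 2.38. It can also hide a retained difference of about 1.1.

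It would go too far to say that the trial's evidence on duration of effect is invalid, or that a comparison of change from the Fixed Dose period is itself improper. The planned pre-treatment-baseline analysis is unaffected, and the arm difference in change from Fixed Dose is protected by randomization as long as the Fixed Dose value is not also a covariate. Importance is modest.

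**What to change.** Amend SAP 4.6.5 to say:

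1. No between-arm model for the withdrawal or washout periods uses the Fixed Dose rate or the end of Fixed Dose measurement as a covariate.
2. The comparison of withdrawal and washout outcomes adjusted for pre-randomization baseline and CSBM stratum stays as planned and is the analysis of persistence.
3. If change from the Fixed Dose period is compared between arms, the model adjusts only for pre-randomization baseline and CSBM stratum, and the result is labelled loss of effect. Keeping this comparison retains the placebo control for time trend and regression to the mean.
4. Change from the Fixed Dose period is also reported within each arm as a mean with 95% CI.

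The cost is SAP wording and a revised specification for the affected tables. No new data, visits or subjects are needed, and the primary analysis does not change.
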